### 4.6.3 Classifications

There are no data-specific classifications in this study (i.e. laboratory).

## 4.7 Handling of Missing Data and Data Imputation

### 4.7.1 Partial Dates

If a date relevant for analysis is only partially available, it will be imputed by the central day of the time period of uncertainty, if this rule will be in line with potential dependencies of other complete dates in chronology. The time period of uncertainty is, for example, the calendar month, if the day is missing, or the calendar year, if day and month are missing. If the imputed date must be before or after a reference date, or between two reference dates, and the central day of the time period of uncertainty would not be, the date will be imputed by the day of the time period of uncertainty closest to the central day but fulfilling the dependencies.

The approach of partial date imputation will be applied to visit dates, start and end dates of adverse events, start and end dates of concomitant medication, and the dates of last study drug application and of last contact, if partial.

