### 4.4.5 Treatment Emergency of Adverse Events

In general, treatment emergent AEs are defined as events starting on or after the day of start of IMP that were absent pre-treatment, or events present prior to the first dose but increased in severity after the first dose. Otherwise, an AE is not treatment-emergent.

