### 5.5.4 Safety Endpoints

Safety endpoints will be described by summary tables on the Safety Analysis Set (SAS).

Treatment-emergent AEs, treatment-emergent drug-related AEs, treatment-emergent serious AEs (SAE), treatment-emergent drug-related SAEs, treatment-emergent AEs leading to drug withdrawal and treatment-emergent drug-related SAEs leading to drug withdrawal will be presented in summary tables of the number and percentage of patients with at least one event, and the number of events, by primary SOC and by PT within SOC. For treatment-emergent AEs and treatment-emergent drug-related AEs, these summaries will also be provided by maximum severity. Maximum severity is defined by the most severe AE per patient, SOC and PT. An overview will summarize incidences in all listed AE categories including deaths.

Vital signs will be summarized by visit including changes from baseline, as well as a shift table with categories: normal, abnormal/non-clinically significant, and abnormal/clinically significant. For physical examination, frequency counts of the complete examination (including all body systems and the vulvar region) at Screening 1 and Week 12 (or EoT) visits as well as the results of the abbreviated physical examination at the baseline and FU visits (if judged necessary by the investigator), will be reported in both

a table with percentages as well as a shift table with categories: normal, abnormal/non-clinically significant, and abnormal/clinically significant. Frequency counts and percentage of urine pregnancy tests will also be presented.

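### SAP 4.7.1 has no conservative default for adverse events of uncertain onset, so its mid-period date rule can class a possibly on-treatment event as pre-treatment

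*SAP*

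**What the plan says.** SAP 4.7.1 (Partial Dates) replaces a partial date by the middle of the month or year in which it must lie: "it will be imputed by the central day of the time period of uncertainty". The rule is conditional: "if this rule will be in line with potential dependencies of other complete dates in chronology". Where the central day breaks a dependency, "the date will be imputed by the day of the time period of uncertainty closest to the central day but fulfilling the dependencies". Adverse events are expressly in scope: "The approach of partial date imputation will be applied to visit dates, start and end dates of adverse events". The section does not name first IMP use as a reference date for AE onset, and it does not deal with a start date that is missing altogether.

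SAP 4.4.5 defines treatment emergence by two limbs. The limb based on onset takes in "events starting on or after the day of start of IMP that were absent pre-treatment". The limb based on worsening takes in "events present prior to the first dose but increased in severity after the first dose". Anything else is not treatment-emergent. Protocol 9.4.3.2 uses the onset date alone.

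Protocol 8.8.4.1 collects AEs from consent to the last visit, and SAP 2.1 places Screening 1 on Day -28 to -8. In SAP Table 6, Tables 14.3.1.2 to 14.3.1.8 cover treatment-emergent events only. Under SAP 5.5.4 the overview covers those same categories plus deaths. Listing 16.2.7.1.1 carries all AEs.

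**The concern.** An AE can validly start between consent and first application. The dependency condition in 4.7.1 therefore does not push an imputed onset up to first use. Take a patient who first applies the cream on the 20th and reports burning in that month with the day missing. If no other complete date intervenes, onset is set to the 15th or 16th and the event becomes pre-treatment.

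The events at risk are those near the start of treatment. Protocol Table 2 plans more frequent AE evaluation in that period, because application site reactions cannot be ruled out in this first use in VLS. A possible early reaction classed as pre-treatment is absent from the AE tables and can be found only by reading the listing.

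**Working it through.** The plan states no figure for this rule, so there is none to reproduce. I enumerated what the rule does.

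**Inputs from the documents.** The central-day rule and its condition (SAP 4.7.1); the emergence definition (SAP 4.4.5); consent 8 to 28 days before Baseline (SAP 2.1); treatment to Day 84 and follow-up to Day 98 (SAP 2.1); 16 to 17 patients per arm (protocol 9.2).

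**Assumptions, not in the documents.** First use is equally likely on each day of the month, and onset on each permissible day. The consent date, where used, is the earliest permissible onset. No AE end date or other record narrows the range. A 30-day month has two middle days and the SAP does not choose, so both are shown.

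**1. When can the error occur (day missing)?** Only if the event falls in the calendar month of first use and first use is after the imputed day. If the event's month is wholly after the month of first use, it is always treatment-emergent. The number of first-use days affected is:
- 30-day month, central day 15: 15/30 = 50%
- 30-day month, central day 16: 14/30 = 47%
- 31-day month, central day 16: 15/31 = 48%

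**2. Share of same-month, on-treatment events misclassified.** Pair each first-use day d = 1..30 with each onset day from d to 30: 30 × 31 / 2 = 465 pairs.
- Central day 15: wrong when d ≥ 16, that is 15 + 14 + ... + 1 = 120 pairs; 120/465 = 25.8%.
- Central day 16: wrong when d ≥ 17, that is 14 + 13 + ... + 1 = 105 pairs; 105/465 = 22.6%.

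**3. Share of all on-treatment events with a missing day.** With central day 15, the misclassifiable days average 120/30 = 4 per patient. With onset uniform to Day 98, 4/98 = 4.1%; to Day 84, 4/84 = 4.8%. Early clustering of events would raise this towards the figure in step 2.

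**4. How uncertain are the cases classed as pre-treatment?** The mean share of permissible onset days that lie on treatment is 25-27% with consent 28 days before first use or no consent bound, and 44-46% with consent 8 days before. Example: 30-day month, central day 16, consent on day 9, first use on day 17. Onset is imputed to day 16, so the event is pre-treatment. Yet 30 - 17 + 1 = 14 of 30 - 9 + 1 = 22 permissible days (64%) are on treatment.

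**5. The opposite error.** Among cases classed as treatment-emergent, a mean of 20-25% of permissible onset days precede first use.

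**6. Only the year known** (2024 as illustration, central day 1 July; permissible onset from consent to 98 days after first use or year end).

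| First use | Consent | Imputed onset | Class | Permissible days on treatment |
|---|---|---|---|---|
| 15 July | 28 days before | 1 July | pre-treatment | 99/127 = 78% |
| 15 July | 8 days before | 7 July (consent) | pre-treatment | 99/107 = 93% |
| 1 October | 28 days before | 3 September (consent) | pre-treatment | 92/120 = 77% |
| 1 October | 8 days before | 23 September (consent) | pre-treatment | 92/100 = 92% |

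First use on 1 March or 1 June gives treatment-emergent. In three of the four rows shown, the dependency condition moves onset to the consent date, which is still before first use.

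**7. Effect on an arm's incidence.** One patient is 1/17 = 5.9 to 1/16 = 6.3 percentage points. SAP 5.5.4 counts patients with at least one event, so the percentage moves only if that patient has no other event in the category.

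**The case against.** The case against a serious finding has several parts.

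- **Few dates should be partial.** Protocol 8.8.4.1 has AEs asked about at each visit, including Days 7 and 18. Protocol 10.1.9.3 has eCRF errors queried, and 10.1.8.2 specifies 100% source data verification. This stands: the number is unknown and probably small.
- **Other complete dates limit the rule.** The AE end date and the date the site became aware of the event (SAP 2.4.2) bound onset. This stands in part. Both are latest possible dates: they can show that onset was early, but they do not move it to first use.
- **The worsening limb of 4.4.5 recovers some events.** It does, but not a new on-treatment event of constant severity. SAP 2.4.2 lists a severity for each AE but no date of change.
- **The rule errs in both directions.** True, as step 5 shows. The consequences differ: over-inclusion leaves the event visible in the tables, while under-inclusion removes it from them.

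A reader might infer that every partially dated AE drops out, that about a quarter of all on-treatment events with a missing day are lost, that everyone starting after mid-month loses all such events, or that each partial date shifts an arm by 6 points. The documents support none of these. The error needs first use after the imputed day in the same month or year, the one-quarter figure applies to same-month events only, and incidence is counted per patient.

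**Conclusion.** The point holds as a limited defect in a stated rule. With no conservative default in 4.7.1 or 4.4.5, the central-day rule can class as pre-treatment an event that may have begun on treatment. Unless the event worsened after first dose, it is then missing from Tables 14.3.1.2 to 14.3.1.8.

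On uniform assumptions, about 23-26% of same-month on-treatment events with a missing day are affected, and about 4-5% of all on-treatment events with a missing day. The absolute number cannot be derived from the documents. A single case can matter in arms of 16 to 17, but only for a patient with no other event in that category. No efficacy analysis is touched, and the events stay in the listing. It deserves correction because the remedy is cheap, not because a large bias is likely.

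**What to change.** Add to SAP 4.7.1, with a cross-reference in 4.4.5: an AE with a partial or missing start date is treated as treatment-emergent, and its start is imputed to the date of first IMP application if the period of uncertainty contains that date. The exception is where the known date parts or another complete date show onset before first application; examples are the AE end date, the date the site became aware, or the visit at which the event was recorded. Keep the central-day rule for other dates.

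The exception is needed. Without it, an ongoing event already recorded at screening in the month of first use would be forced onto treatment. With the rule in place, no event that could have begun on treatment is classed as pre-treatment, by construction.

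In the same edit, state that the sentence in SAP 4.7.2 ruling out imputation on the safety set does not refer to dates.

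The cost is about one sentence of SAP text and a small programming change, best settled before unblinding. The downside is that a few events that truly began before treatment may be counted as treatment-emergent, in either arm.

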### 4.7.2 Missing Data

Data is missing if unavailable. Data is invalid if not considered for analysis. Invalidity of data is defined below, where applicable. On some analyses as indicated below, missing or invalid data will be replaced by multiple imputation (MI).

For analyses on MFAS, PPS, and SAS, no imputations will be made for missing data. Of the three different analyses on FAS, in one analysis MI will be implemented for missing and invalid data.

#### Multiple Imputation

Post-baseline missing or invalid data will be multiply imputed within treatment groups in two steps [10]. At first, any potential intermediate missing data will be imputed 20 times using a Markov Chain Monte Carlo (MCMC) method to obtain a monotone missing data pattern. In a second step, imputation is done using a monotone regression method, fitting an analysis of covariance (ANCOVA) model stepwise visit by visit. The ANCOVA model adjusts for the effects of menopausal status at baseline, ICIQ-UI-SF score at baseline as factors, and the baseline value of the respective endpoint as a covariate. For each treatment group and each copy of the dataset, the estimated parameters and their variances are used to impute the endpoint. Starting with Week 1, the procedure is repeated on Week 4, Week 8 and Week 12, adding the possibly imputed values of the previous visits as covariates. On MI, missing score data is handled like missing continuous data.

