### Skindex-29

Skindex-29 is a skin specific multidimensional quality-of-life instrument. It must be evaluated by the patient, concentrating on their vulvar area, at Baseline, Week 4, Week 8, and Week 12 (or EoT) visits using the Skindex-29 Quality of Life Index questionnaire. It inquires how often (1. Never, 2. Rarely, 3. Sometimes, 4. Often, 5. All the time) during the previous 4 weeks the patient experienced the effect described in each item. Seven items address the Symptoms domain, ten items the Emotions domain, and twelve items the Functioning domain. All responses are transformed to a linear scale of 100, varying from 0 (no effect) to 100 (effect experienced all the time) as 25 times (score-1). Skindex-29 scores are reported as three scale scores, corresponding to the three domains; a scale score is the average of a patient's non-missing responses to items in a given domain [7]. The questionnaire comprises 30 items; however, Item 18 is excluded from the Skindex-29 score as per the guidelines of the originators of the test. If any scale has more than 25% of the responses missing, the scale is missing.

Table 1 Skindex-29 domains and their items

Functioning	Emotions	Symptoms
2. MSC affects how well I sleep	3. I worry that MSC may be serious	1. My skin hurts
4. MSC makes it hard to work or do hobbies	6. MSC makes me feel depressed	7. MSC burns or stings
5. MSC affects my social life	9. I worry about getting scars from MSC	10. My skin itches
8. I tend to stay at home because of MSC	12. I am ashamed of MSC	16. Water bothers MSC (bathing, washing hands)
11. MSC affects how close I can be with those I love	13. I worry that MSC may get worse	19. My skin is irritated
14. I tend to do things by myself because of MSC	15. I am angry about MSC	24. My skin is sensitive
17. MSC makes showing affection difficult	21. I am embarrassed by MSC	27. MSC bleeds
20. MSC affects my interactions with others	23. I am frustrated by MSC	
22. MSC is a problem for the people I love	26. I am humiliated by MSC	
25. MSC affects my desire to be with people	28. I am annoyed by MSC	
29. MSC interferes with my sex life		
30. MSC makes me tired		

MSC = My skin condition

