### 5.4.1 Binary Data

The binary secondary endpoints (Section 2.4.1) will be analysed using a logistic model with effects of treatment, menopausal status at baseline, ICIQ-UI-SF score at baseline, and the baseline value for each scale the binary endpoint is derived from (WI-NRS or WP-NRS) as factors. The estimated log odds ratios between the treatments at Week 12 will be derived together with the associated standard error and 95% confidence intervals. These binary endpoints will be summarized in descriptive tables and visualized in bar charts, in both cases stratified by treatment group and visit.

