#### Mixed Model of Repeated Measures (MMRM)

Comparisons will be done using an MMRM model including treatment, visit, treatment-by-visit interaction, as factors, and menopausal status at baseline, ICIQ-UI-SF score at baseline, and the baseline value of the respective endpoint as covariates.

The statistical model is

$$\text{Endpoint} = \beta_0 + \beta_1 \text{Otreatment} + \beta_2 \text{OVisit} + \beta_3 \text{OTreatment-by-visit} + \beta_4 \text{Omenopausal status} + \beta_5 \text{OICIQ-UI-SF score} + \beta_6 \text{Obaseline value} + \text{error},$$

where  $\beta_1$  -  $\beta_6$  are parameters of fixed effects and  $\beta_0$  an intercept. The estimated treatment differences between MC2-25 cream and MC2-25 vehicle, will be reported together with the associated standard error, the 95% confidence interval, and a p-value of a test on the respective contrast corresponding to the hypothesis of no difference between treatments (superiority) (Section 5.2).

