### 5.5.2 Secondary Endpoints

The secondary endpoints follow two quite different analysis strategies.

The two continuous endpoints (all defined from Baseline to Week 12):

- Mean change in weekly mean Worst Pain Numeric Rating Score (WP-NRS) recorded in the patient's diary (Weekly mean WP-NRS is calculated as the average of WP-NRS values recorded in the patient's diary for 7 days prior to the in-clinic visits.)
- Change in Skindex-29 domains

will be analysed in an identical fashion to the primary endpoint described in Section 5.5.1, which includes one analysis on the FAS with imputation, and a further four sensitivity analyses, all without imputation.

The four binary endpoints (all defined from Baseline to Week 12):

- Percentage of patients obtaining a  $\geq 4$ -point improvement in weekly mean WI-NRS recorded in the patient's diary
- Percentage of patients obtaining a  $\geq 4$ -point improvement in weekly mean WP-NRS recorded in the patient's diary
- Percentage of patients obtaining a  $\geq 3$ -point improvement in weekly mean WI-NRS recorded in the patient's diary
- Percentage of patients obtaining a  $\geq 3$ -point improvement in weekly mean WP-NRS recorded in the patient's diary

will be analysed using the treatment policy strategy on the FAS in a logistic regression model with a factor for treatment, and covariates menopausal status at baseline, ICIQ-UI-SF score at baseline, as well as the baseline value of the scale the binary endpoint is derived from (WI-NRS or WP-NRS). The estimated log odds ratios between treatments at Week 12 will be reported, along with the 95% confidence interval. The logistic regression models will be carried out on worst case imputation data, where missing endpoint data is assumed to be no response.

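### SAP 4.7.2 lists the 0–21 ICIQ-UI-SF score as a factor in the within-arm imputation model, while SAP 5.4.3 lists it as a covariate; the plan should fix its coding at one degree of freedom

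*SAP*

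**What the plan says.** SAP 4.7.2 begins: "Post-baseline missing or invalid data will be multiply imputed within treatment groups in two steps". The second step is a regression fitted visit by visit at Weeks 1, 4, 8 and 12, with earlier visits added as predictors. Of that model it says: "The ANCOVA model adjusts for the effects of menopausal status at baseline, ICIQ-UI-SF score at baseline as factors". The same sentence then calls only the baseline value of the endpoint a covariate. SAP 2.4.1 defines the ICIQ-UI-SF score as a sum of three items ranging from 0 to 21. SAP 4.7.2 gives no cut or grouping for it.

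SAP 5.4.3 describes the MMRM as "including treatment, visit, treatment-by-visit interaction, as factors", followed by "menopausal status at baseline, ICIQ-UI-SF score at baseline, and the baseline value of the respective endpoint as covariates". For the four responder endpoints, SAP 5.4.1 lists treatment, menopausal status, the ICIQ-UI-SF score and "the baseline value for each scale the binary endpoint is derived from (WI-NRS or WP-NRS) as factors". SAP 5.5.2 describes the same logistic model with "covariates menopausal status at baseline, ICIQ-UI-SF score at baseline, as well as the baseline value of the scale".

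Protocol 9.4.2.1 names the score without saying how it is coded. The protocol synopsis speaks instead of incontinence status, with the score in brackets.

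SAP 5.5.1 makes the FAS analysis with multiple imputation primary. SAP 5.5.2 adds that the change in WP-NRS and in the Skindex-29 domains "will be analysed in an identical fashion to the primary endpoint described in Section 5.5.1".

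**The concern.** SAP 4.7.2 and 5.4.3 each separate factors from covariates within one sentence, and they put the ICIQ-UI-SF score on opposite sides. A programmer who follows 4.7.2 as written would declare a score with up to 22 values (0 to 21) as a class variable, in a model fitted to at most 16 or 17 patients.

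Each distinct score beyond the first then takes one coefficient. With few residual degrees of freedom, the draws of the residual variance and the coefficients become erratic, so the imputed values scatter and the between-imputation variance rises. With none left, there is no residual variance to draw from. A patient with missing data whose score does not occur among the observed patients in her arm has no estimable level effect at all.

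This model feeds the primary p-value and, through SAP 5.5.2, the continuous secondary endpoints.

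**Working it through.** **The plan's own figure.** Protocol 9.2 states power of at least 78% for 16 to 17 per arm, an effect of 1 SD and a two-sided 5% test. A two-sample t-test (noncentral t) gives 78.1% for 16/16, 79.4% for 16/17 and 80.7% for 17/17. The figure is reproduced; it assumes complete data.

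**Parameters in the Week 12 imputation step, within one arm (WI-NRS, WP-NRS).**
- Score as a factor: intercept 1 + menopausal status 1 + ICIQ-UI-SF (L − 1) + baseline 1 + Weeks 1, 4 and 8, 3 = L + 5. Residual df = n_obs − 5 − L.
- Score as one linear term: 1 + 1 + 1 + 1 + 3 = 7. Residual df = n_obs − 7.
- Difference: L − 2. It is zero for a two-level variable.

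| n_obs | L = 5 | L = 8 | L = 10 | linear |
|---|---|---|---|---|
| 15 | 5 | 2 | 0 | 8 |
| 16 | 6 | 3 | 1 | 9 |
| 17 | 7 | 4 | 2 | 10 |

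The ranks of simulated design matrices agree with these formulas wherever the df are not negative. Skindex-29 is completed "at Baseline, Week 4, Week 8, and Week 12 (or EoT) visits using the Skindex-29 Quality of Life Index questionnaire", so it has no Week 1 value. Its counts are n_obs − 4 − L and n_obs − 6.

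**How large L might be.** The documents do not say. If 20–50% of patients score 0 and the rest are uniform on 3–12 or on 1–21, then with 16–17 observed the mean L is about 6.6 to 11.1. The mean residual df is about 5.2 down to 0.3.

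**Illustrative effect on power.** Inputs from the documents: 17 versus 16 patients, a true effect of 1 SD, 20 imputations, and incontinence rates of 34% and 63% (Protocol 2.2.1, women without and with LS). Assumed inputs:
- change SD 2, with correlation 0.7 to the power of the visit lag;
- 70% menopausal; baseline mean 6.5, SD 1.5, cut to 4–10;
- random monotone dropout after Week 1, 4 or 8;
- positive scores uniform on 3–8, or normal (mean 9, SD 4) on 3–21;
- an unstructured covariance by REML and Barnard–Rubin df, which the SAP does not state.

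An unseen score was put at the reference level, also an assumption; this arose in 22–44% of trials with 2 missing. There were 2,000 trials per cell (Monte Carlo error about 1 point). Power in %, factor versus linear, is on trials where the factor imputation can run:

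| Scenario | 1 missing | 2 missing | 3 missing | 5 missing |
|---|---|---|---|---|
| 34%, 3–8 | 71 v 73 | 65 v 68 | 58 v 66 | 41 v 55 |
| 34%, 3–21 | 66 v 70 | 60 v 69 | 53 v 65 | 32 v 52 |
| 63%, 3–8 | 66 v 73 | 58 v 71 | 45 v 63 | 24 v 56 |
| 63%, 3–21 | 52 v 72 | 37 v 69 | 27 v 66 | 13 v 53 |

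The factor imputation cannot run in 9/15/26/47% of trials in the last row, and in 0–3% in the others. The median ratio of pooled standard errors (factor/linear) is 1.02/1.04/1.06/1.13 in the first row and 1.11/1.31/1.56/2.18 in the last. With complete data, power is 74–78%. Type I error with 2 or 5 missing is 0.4–3.7% for the factor coding and 2.5–4.4% for the linear term. A second simulation with a simpler Week 12 ANCOVA gave similar standard error ratios for 2/3/5 missing: 1.04/1.07/1.14 in the first scenario and 1.31/1.55/2.08 in the last.

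**Logistic model.** With an assumed response of 60% versus 30% and 300 trials per scenario, no finite treatment odds ratio exists in 82–97% of trials if the score and baseline NRS are both factors as in 5.4.1. With both as covariates it is 0.3–1.3%.

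**The case against.** The strongest reply is that the many-level coding was never meant. The protocol synopsis names incontinence status, Protocol 4.2.4 says that status can be taken into account in the analysis, and both documents give a score of 1 or more as the mark of incontinence. A two-level factor has L = 2 and costs no degrees of freedom against a linear term. This reading is plausible but not established: SAP 4.7.2 says score and gives no cut.

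The SAP also uses the two words loosely. SAP 5.4.1 calls even the baseline NRS a factor, and SAP 5.4.3 calls two-level menopausal status a covariate. SAP 3.2.2 groups scores with continuous data, though for summaries. SAP 5.7 leaves technical detail to programming specifications that are not part of these documents. All this makes a slip likely; none of it fixes the coding.

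A reader might infer that SAP 5.4.3 proves a linear term, so that 4.7.2 is simply wrong. It does not. Besides the point about menopausal status, its equation gives visit and treatment-by-visit one coefficient each, although there are four post-baseline visits.

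The harm is also bounded. Protocol 7.1 encourages patients who stop treatment to keep attending visits, which should limit missing data. The trial is exploratory. For the responder endpoints, SAP 5.5.2 already gives workable wording.

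**Conclusion.** The point holds as an inconsistency that should be resolved: SAP 4.7.2, followed literally, gives a worse primary analysis than a one-degree-of-freedom term. The df counts follow from the stated model alone. The power losses do not. They rest on assumed score distributions, missingness and handling of unseen scores, and run from about 2 points (one missing patient, few score levels) to tens of points (several missing, widely spread scores), where the model may not run at all.

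Two stronger inferences are not supported. One is that the literal coding invites false claims: the simulated type I error stays below 5%. The other is that the primary analysis is bound to lose much power: with no missing post-baseline data nothing changes, and sensitivity analysis (a), the FAS MMRM without imputation, is untouched in any case.

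**What to change.** Before unblinding:
- State in SAP 4.7.2 that the baseline ICIQ-UI-SF score enters the imputation model with a single degree of freedom, as one continuous covariate. This matches the score named in Protocol 9.4.2.1 and SAP 5.4.3. If incontinence status is what is meant, state the two-level indicator with the cut at 1 or more instead.
- State the same coding for the MMRM in SAP 5.4.3.
- In SAP 5.4.1, replace the factor wording with that of 5.5.2, so that the baseline NRS is a continuous covariate and ICIQ-UI-SF is coded as in the other models.

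The cost is a sentence and small wording changes, with no effect on patients or procedures. The downside is an assumption of linearity in the score or, with the indicator, the detail lost by the cut.
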